5.1 Treatments Administered

- Rovalpituzumab tesirine 0.3 mg/kg IV on Day 1 of the first and third 3-week cycle (q6wk x 2), or per other dosing regimen recommended by the SMC (all cohorts)
- Nivolumab 360 mg IV q3wk x 2 cycles beginning on Week 4 (Cycle 2) (Cohort 1)
- Nivolumab 1 mg/kg IV q3wk x 4 cycles (Cohorts 2 and 3)
- Nivolumab 480 mg q4wk (all cohorts) – monotherapy to be given after a washout period from ipilimumab. See study drug dosing schedule (Section 5.1.1)
- Ipilimumab 1 mg/kg IV q3wk x 4 cycles beginning on Week 4 (Cycle 2) (Cohort 2)
- Ipilimumab 3 mg/kg IV q3wk x 4 cycles beginning on Week 4 (Cycle 2) (Cohort 3)
- Dexamethasone 8 mg orally (PO) twice daily (BID) on Day -1, Day 1 (the day of dosing), and Day 2 of each cycle in which rovalpituzumab tesirine is administered (all cohorts)

On applicable cycles, rovalpituzumab tesirine will be administered before nivolumab and ipilimumab. Similarly, on applicable cycles, nivolumab will be administered prior to ipilimumab.

Detailed information describing the preparation, administration, and storage of rovalpituzumab tesirine, nivolumab, and ipilimumab is located in the Pharmacy Binder.

5.1.1 Treatment Regimen Descriptions for Each Cohort

The schedule, dose, route, and cycle length for the treatment regimens in each of the three cohorts are summarized below in [Table 2](#).

Table 2. Study Drug Dosing Schedule

Cohort	Study Drug(s)	Cycle					
		1	2	3	4	5	6+
1 ^a	Rovalpituzumab tesirine 0.3 mg/kg	X		X			
	Nivolumab 360 mg q3wk		X	X			
	Nivolumab 480 mg q4wk				X	X	X
2 ^b	Rovalpituzumab tesirine 0.3 mg/kg	X		X			
	Nivolumab 1 mg/kg		X	X	X	X	
	Ipilimumab 1 mg/kg		X	X	X	X	
	Nivolumab 480 mg q4wk ^d						X
3 ^c	Rovalpituzumab tesirine 0.3 mg/kg	X		X			
	Nivolumab 1 mg/kg		X	X	X	X	
	Ipilimumab 3 mg/kg		X	X	X	X	
	Nivolumab 480 mg q4wk ^e						X

- a) Cycles 1–3 are 3 weeks. Cycles 4 and beyond are 4 weeks.
- b) Cycles 1–5 are 3 weeks. Cycles 6 and beyond are 4 weeks
- c) Cycles 1–5 are 3 weeks. Cycles 6 and beyond are 4 weeks
- d) Nivolumab 480 mg q4wk (monotherapy) to be started 6 weeks after Cycle 5 Day 1 in Cohort 2.
- e) Nivolumab 480 mg q4wk (monotherapy) to be started 8 weeks after Cycle 5 Day 1 in Cohort 3.

5.2 Investigational Product (Rovalpituzumab Tesirine)

5.2.1 Description

Rovalpituzumab tesirine (SC16LD6.5) drug product is provided in a sterile clear United States Pharmacopeia (USP) Type I 10 mL glass vial as a lyophilized powder containing 30 mg/vial. The lyophilized drug product is reconstituted with 3.2 mL sterile water for injection to deliver 3 mL per vial of 10 mg/mL rovalpituzumab tesirine. The rovalpituzumab tesirine formulation consists of 10 mg/mL rovalpituzumab tesirine in 20 mM histidine hydrochloride, 0.175 M sucrose and 0.4 mg/mL polysorbate 20, pH 6.0. The lyophilized drug product is stored and shipped at 2-8°C prior to its use in clinical trials.

A description of the chemistry and formulation may be found in the Investigator's Brochure (IB).

5.2.2 Packaging and Labeling

Rovalpituzumab tesirine is provided in sterile clear USP Type I, 10 mL glass vials. The vials and/or primary vial carton will have labels bearing the appropriate label text as required by governing regulatory agencies.

5.2.3 Dosing and Administration

Dosing is based on subject actual body weight to the nearest tenth of a kilogram, assessed on Day 1 of each cycle, and administered according to the assigned dose. Detailed information describing the preparation, administration, and storage of rovalpituzumab tesirine is located in the Pharmacy Binder.

Subjects must meet all of the following on each dosing day before receiving rovalpituzumab tesirine:

- ANC \geq 1,000/ μ L
- Platelet count \geq 100,000/ μ L
- Resolution to Grade 0 or 1, or to baseline grade if pre-existing, of any clinically-significant clinical or laboratory AE (excluding alopecia) occurring during the previous cycle, including findings indicative of pleural or pericardial effusions.

5.3 Investigational Product (Nivolumab; Opdivo[®])

5.3.1 Description, Packaging and Labeling

Nivolumab, available in the United States as Opdivo, is a sterile, preservative-free, non-pyrogenic, clear to opalescent, colorless to pale-yellow liquid that may contain light (few) particles. Opdivo injection for intravenous (IV) infusion is supplied in single-dose vials. Each mL of Opdivo solution contains nivolumab 10 mg, mannitol (30 mg), pentetic acid (0.008 mg), polysorbate 80 (0.2 mg), sodium chloride (2.92 mg), sodium citrate dihydrate (5.88 mg), and Water for Injection, USP. May contain hydrochloric acid and/or sodium hydroxide to adjust pH to 6 (BMS, 2016). Additional details or updates may be found in the most recent Prescribing Information.

5.3.2 Dosing and Administration

Detailed information describing the preparation, administration, and storage of nivolumab is located in the Pharmacy Binder.

5.4 Investigational Product (Ipilimumab; Yervoy[®])

5.4.1 Description, Packaging and Labeling

Ipilimumab, available in the United States as Yervoy, is a sterile, preservative-free, clear to slightly opalescent, colorless to pale yellow solution for IV infusion, which may contain a small amount of visible translucent-to-white, amorphous ipilimumab particulates. It is supplied in

single-use vials of 200 mg/40 mL. Each milliliter contains 5 mg of ipilimumab and the following inactive ingredients: diethylene triamine pentaacetic acid (DTPA) (0.04 mg), mannitol (10 mg), polysorbate 80 (vegetable origin) (0.1 mg), sodium chloride (5.85 mg), tris hydrochloride (3.15 mg), and Water for Injection, USP at a pH of 7 (BMS, 2015). Additional details or updates may be found in the most recent Prescribing Information.

5.4.2 Dosing and Administration

Detailed information describing the preparation, administration, and storage of ipilimumab is located in the Pharmacy Binder.

5.5 Dose Delays/Modifications (Nivolumab and Ipilimumab)

5.5.1 Dose Delay Criteria (Nivolumab and Ipilimumab)

Dose reductions for nivolumab and ipilimumab are not permitted in this study. Nivolumab monotherapy or both nivolumab together with combination therapy should be delayed for the following:

- Any Grade ≥ 1 pneumonitis
- Any Grade ≥ 2 non-skin, drug-related AE, with the following exceptions:
 - Grade 2 drug-related fatigue or laboratory abnormalities do not require a treatment delay.
- Grade 2 drug-related creatinine, AST, ALT, or total bilirubin abnormalities
- Any Grade ≥ 3 skin drug-related AE
- Any Grade 3 drug-related laboratory abnormality with the following exceptions:
 - Grade 3 or 4 lymphopenia does not require a dose delay
 - Any Grade 3 drug-related amylase and/or lipase abnormality that is not associated with symptoms or clinical manifestations of pancreatitis does not require dose delay.

Any AE, laboratory abnormality or inter-current illness which, in the judgment of the investigator, warrants delaying the dose of study medication. In the event of isolated CNS progression during study treatment, study drug(s) may be withheld while palliative treatment is administered, e.g. a standard course of whole brain radiotherapy in accordance with institutional practice, and restarted within 1 week after completion of radiotherapy. During this time the subject should be fully evaluated for other sites of disease progression. If more than 6 weeks have elapsed since the previous dose of study drug(s), the subject should undergo a radiographic tumor assessment before restarting study drugs. If additional sites of PD are present, the subject

will be required to discontinue study drugs (but may be eligible for re-treatment as per Section 3.1.2).

If the decision is made to resume nivolumab and/or ipilimumab dosing, the subject should restart treatment on the next regularly scheduled dosing visit. Skipped doses are not to be replaced. If treatment is delayed >6 weeks, the subject must be permanently discontinued from all study therapy, except as specified in Dose Discontinuation Criteria. Tumor assessments for all subjects should continue as per protocol **even if dosing is delayed**.

5.5.2 Criteria to Resume Nivolumab/Ipilimumab Dosing

Subjects will be permitted to resume therapy at the same dose level(s) following resolution of the AE to \leq Grade 1 or to baseline within 6 weeks after the last dose, with the exception of subjects who meet criteria for permanent discontinuation as specified in Section 5.5.4 (Dose discontinuation criteria below). Subjects who meet criteria for permanent discontinuation must not receive further study therapy.

Subjects may resume treatment with nivolumab and/or ipilimumab when the drug-related AE(s) resolve(s) to Grade \leq 1 or baseline, with the following exceptions:

- Subjects may resume treatment in the presence of Grade 2 fatigue.
- For subjects with Grade 2 AST, ALT, or total bilirubin elevations, dosing may resume when laboratory values return to baseline and management with corticosteroids, if needed, is complete.
- Subjects with combined Grade 2 AST/ALT AND total bilirubin values meeting discontinuation parameters (Section 5.5.4) should have treatment permanently discontinued.
- Drug-related pulmonary toxicity, diarrhea, or colitis must have resolved to baseline before treatment is resumed. Subjects with persistent Grade 1 pneumonitis after completion of a steroid taper over at least 1 month may be eligible for re-treatment if discussed with and approved by the sponsor and/or medical monitor.
- Drug-related endocrinopathies adequately controlled with only physiologic hormone replacement may resume treatment after consultation with the sponsor and/or medical monitor.
- Dose delay of nivolumab or ipilimumab that results in treatment interruption of >6 weeks requires treatment discontinuation, with exceptions as noted in Section 5.5.4. However, if the toxicity resolves to \leq Grade 1 or baseline >6 weeks after the last dose, but the subject does not otherwise meet the criteria for permanent discontinuation (Section 5.5.4), and the investigator

believes that the subject is deriving clinical benefit, then the subject may be eligible to resume the study drug(s) following the approval of the sponsor and/or medical monitor.

5.5.3 Rovalpituzumab Tesirine Dose Delays/Modifications

In general, if a subject has a clinically significant, unresolved AE on the next scheduled dosing day, treatment with rovalpituzumab tesirine may be delayed for up to 21 days. The AE must resolve to baseline or \leq Grade 1 prior to proceeding with treatment, unless the AE is determined to be clearly unrelated to rovalpituzumab tesirine. In cases of treatment delays of >21 days for unresolved adverse events, the medical monitor should be contacted regarding the subject's continuation of treatment.

If rovalpituzumab tesirine is delayed at Cycle 3 Day 1, nivolumab and/or ipilimumab are not required to be delayed.

In general, subjects who experience a clinically-significant Grade 3 or 4 AE (unless the AE is determined to be clearly unrelated to rovalpituzumab tesirine) should have a dose reduction(s) of rovalpituzumab tesirine in subsequent treatment cycles to dose level -1 or -2 , or as suggested upon discussion with the medical monitor and/or sponsor. If the clinically-significant Grade 3 or 4 AE recurs after dose reduction, rovalpituzumab tesirine should be permanently discontinued.

5.5.4 Permanent Treatment Discontinuation Criteria

Subjects meeting any of the following criteria will be required to permanently discontinue all assigned study drug(s).

- PD (see details regarding continuing treatment beyond initial assessment of progression per RECIST v1. 1). See Section 7.2.1 for additional details.
- Clinical deterioration, as assessed by the investigator
- Any Grade 2 drug-related uveitis or eye pain or blurred vision that does not respond to topical therapy and does not improve to Grade 1 severity within 6 weeks OR requires systemic treatment
- Any Grade ≥ 2 drug-related pneumonitis or interstitial lung disease that does not resolve following dose delay and systemic steroids (also see Pulmonary Adverse Event Management Algorithm);
- Any Grade 3 non-skin, drug-related AE lasting >7 days or recurs, with the following exceptions:
 - Grade 3 drug-related uveitis, pneumonitis, bronchospasm, hypersensitivity reaction, or infusion reaction of any duration requires discontinuation

- Grade 3 drug-related endocrinopathies adequately controlled with only physiologic hormone replacement do not require discontinuation
- Grade 3 drug-related laboratory abnormalities do not require treatment discontinuation except:
 - Grade 3 drug-related thrombocytopenia >7 days or associated with bleeding requires discontinuation
 - Grade ≥ 3 drug-related AST, ALT or Total Bilirubin requires discontinuation
 - In most cases of Grade 3 AST or ALT elevation, study drug(s) will be permanently discontinued. If the investigator determines a possible favorable benefit/risk ratio that warrants continuation of study drug(s), a discussion between the investigator and the Medical Monitor/designee must occur
- Any Grade 4 drug-related AE or laboratory abnormality (including but not limited to creatinine, AST, ALT, or Total Bilirubin), except for the following events which do not require discontinuation:
 - Grade 4 neutropenia ≤ 7 days
 - Grade 4 lymphopenia or leukopenia
 - Isolated Grade 4 amylase and/or lipase abnormalities that are not associated with symptoms or clinical manifestations of pancreatitis
 - Isolated Grade 4 electrolyte imbalances/abnormalities that are not associated with clinical sequelae and are corrected with supplementation/appropriate management within 72 hours of their onset
- Any AE, laboratory abnormality, or intercurrent illness, which, in the judgment of the investigator, presents a substantial clinical risk to the subject with continued treatment.
- Any dosing delay of nivolumab or ipilimumab lasting >6 weeks after the last dose, with the following exceptions:
 - Dosing interruptions to allow for prolonged steroid tapers to manage drug-related AEs are allowed. Prior to re-initiating treatment in a subject with a dosing interruption lasting >6 weeks after the last dose and with no more than 3 missed doses, the medical monitor must be consulted. Tumor assessments should continue as per protocol even if dosing is interrupted.
 - Dosing interruptions >6 weeks after the last dose, which occur for non-drug-related reasons, may be allowed if approved by the medical monitor. Prior to re-initiating treatment in a subject with a dosing interruption lasting >6 weeks after the last dose and

with no more than 3 missed doses, the medical monitor must be consulted. Tumor assessments should continue as per protocol even if dosing is interrupted, and subjects must otherwise meet the criteria for continued treatment at the time re-initiation of study therapy is considered.

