6.4.5 Washout Period Safety Assessments

After the last dose of ipilimumab has been administered on Cycle 5 Day 1 in Cohorts 2 and 3, the subject will undergo a washout period for 6 weeks if in Cohort 2, and 8 weeks if in Cohort 3. During the washout period, subjects will have a Safety Visit in clinic and telephone follow-up calls as described in Table 3 and Table 4.

Table 3. Cohort 2 Washout Period Schedule

Study Drug	Cycle 5 Day 1	Washout Period						Cycle 6 Day 1 ^b
		Week 1	Week 2 ^a	Week 3	Week 4 ^a	Week 5		
Nivolumab 1 mg/kg	X		Safety Visit		Phone Follow-up			
Ipilimumab 1 mg/kg	X							
Nivolumab 480 mg q4wk				X				

- a. Window for visit/telephone follow-up is ± 3 days.
 b. Window for visit is ± 2 days.

Table 4. Cohort 3 Washout Period Schedule

Study Drug	Cycle 5 Day 1	Washout Period							Cycle 6 Day 1 ^b
		Week 1	Week 2 ^a	Week 3	Week 4 ^a	Week 5	Week 6 ^a	Week 7	
Nivolumab 1 mg/kg	X		Safety Visit		Phone Follow Up Visit		Safety Visit		
Ipilimumab 3 mg/kg	X								
Nivolumab 480 mg q4wk				X					

- a. Window for visit/telephone follow-up is ± 3 days.
 b. Window for visit is ± 2 days.

Safety Visit

The following will be performed during the Safety Visit:

- Physical examination (Section 7.7.1)
- Vital signs (Section 7.7.2)
- ECOG performance status (Appendix 13.3)
- Record AEs and SAEs (Section 7.6)
- Record concomitant medications
- Blood samples for:
- CBC with differential (Section 7.7.3)
- Serum chemistries (Section 7.7.3)

Telephone Follow-up Calls

The following will be reviewed during the telephone follow-up call:

- Any new or ongoing AEs
- Any new concomitant medications

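### The 6-week limit on nivolumab/ipilimumab delays ignores the planned 6- and 8-week washouts, so a short adverse-event hold at Cycle 6 can literally require permanent discontinuation

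*Combined protocol and SAP*

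**What the plan says.** Three sections of the protocol set a 6-week limit on interrupting nivolumab or ipilimumab.

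- **Section 5.5.1** measures how long treatment is held: "If treatment is delayed >6 weeks, the subject must be permanently discontinued from all study therapy, except as specified in Dose Discontinuation Criteria".
- **Section 5.5.2** first makes resumption depend on the adverse event settling (Grade 1 or lower, or baseline) no later than six weeks from the most recent dose. It repeats that a longer interruption means stopping, and refers to the Section 5.5.4 exceptions. It then adds a route of its own. If the toxicity settles only after six weeks from the last dose, no other permanent-stop criterion is met and the investigator sees clinical benefit, "then the subject may be eligible to resume the study drug(s) following the approval of the sponsor and/or medical monitor".
- **Section 5.5.4** requires all assigned study drugs to be stopped for good if a listed criterion is met. One criterion is "Any dosing delay of nivolumab or ipilimumab lasting >6 weeks after the last dose". It has two exceptions. The first is "Dosing interruptions to allow for prolonged steroid tapers to manage drug-related AEs are allowed". The second covers interruptions for non-drug-related reasons, if the medical monitor approves.

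The dosing schedule contains a long planned gap after the last combination dose. Section 6.4.5 says that "the subject will undergo a washout period for 6 weeks if in Cohort 2, and 8 weeks if in Cohort 3". Table 2 agrees; its note for Cohort 3 reads "Nivolumab 480 mg q4wk (monotherapy) to be started 8 weeks after Cycle 5 Day 1 in Cohort 3". The window for the Cycle 6 Day 1 visit is ±2 days (Tables 3 and 4).

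Sections 5.5.1, 5.5.2 and 5.5.4 do not mention the washout.

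**The concern.** A limit counted from the last dose works when the planned interval is well below the limit. Here the planned interval equals the limit in Cohort 2 and exceeds it in Cohort 3. A subject who needs a genuine hold at Cycle 6 therefore starts it with the allowance already used up. Whether that subject must stop, may resume freely, or may resume with approval depends on which section the site follows.

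Safety is the primary objective. Permanent discontinuations with reasons (Section 10.3.1) and exposure (Section 10.3.3) are reported by cohort. If sites resolve the conflict differently, or follow the Section 5.5.4 clock literally, some Cohort 3 discontinuations around Cycle 6 would reflect the wording of the rule rather than the tolerability of the regimen. The same event could also be recorded as a protocol deviation at one site and as compliant at another.

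**Working it through.** **Inputs.** Limit: more than 6 weeks (5.5.1, 5.5.2, 5.5.4). Planned gap from Cycle 5 Day 1 to Cycle 6 Day 1: 6 weeks in Cohort 2 and 8 weeks in Cohort 3 (Table 2 notes d and e; 6.4.5). Visit window: ±2 days. Other planned intervals: 3 and 4 weeks (Table 2).

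**1. Reproduce the planned gaps.** Tables 3 and 4 show five and seven washout weeks before Cycle 6 Day 1. That puts the visit at 5 + 1 = 6 weeks and 7 + 1 = 8 weeks, as in Table 2. In days: 6 × 7 = 42 (window 40 to 44) and 8 × 7 = 56 (window 54 to 58).

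**2. Compare with the limit under each clock.** The limit is 6 × 7 = 42 days and is first exceeded on day 43. Room left on the due date under the last-dose clock is 42 minus the planned interval. Under the length-of-delay clock, the limit falls at the planned interval plus 42 days.

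| Planned interval | Room, last-dose clock | Limit reached, length-of-delay clock |
|---|---|---|
| 3 weeks | 42 − 21 = 21 days | 21 + 42 = day 63 |
| 4 weeks | 42 − 28 = 14 days | 28 + 42 = day 70 |
| Cohort 2 washout | 42 − 42 = 0 days (+2 to −2 over the window) | 42 + 42 = day 84 |
| Cohort 3 washout | 42 − 56 = −14 days (−12 to −16) | 56 + 42 = day 98 |

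An on-time Cohort 2 dose falls on day 42, which is not more than 42. Only days 43 and 44 of its window lie beyond the limit.

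**3. Follow one subject through the text.** Take a Cohort 3 subject with a Grade 2, non-skin, drug-related clinical event on Cycle 6 Day 1 (day 56), of a kind that Section 5.5.1 says requires a hold. Assume that no steroid taper is needed and, for illustration, that the event settles after 5 days, on day 61.

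- Section 5.5.1: the delay is 5 days, below 42, so no stop is required.
- Section 5.5.4: 61 exceeds 42, so the criterion is met. The event is drug-related and has no steroid taper, so neither exception applies.
- Section 5.5.2: the basic condition fails, since 61 exceeds 42. The added route may still allow resumption with approval, but Section 5.5.4 does not list it.

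Section 5.5.1 also says that dosing restarts at the next routine dosing visit. If that is 28 days later, the restart is on day 56 + 28 = 84, a delay of 28 days. The three answers do not change. In Cohort 2 the same event settles on day 42 + 5 = 47, again beyond 42.

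**4. Events arising late in the Cohort 3 washout.** The washout runs 56 − 42 = 14 days past the limit. An event that first appears in those 14 days, after the Week 6 safety visit in Table 4, cannot settle by day 42. The basic Section 5.5.2 condition is therefore impossible to meet.

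**5. What is not touched.** Cycles 1 to 4 last 4 × 21 = 84 days, so Cycle 5 Day 1 is Day 85 and the washout follows the 12-week DLT period. Cycle 6 Day 1 is Day 85 + 42 = 127 (Cohort 2) or 85 + 56 = 141 (Cohort 3).

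**The case against.** The strongest reply is that a scheduled washout is not a dosing delay. Section 5.5 is about doses withheld for adverse events, laboratory findings, intercurrent illness or CNS progression, and a subject dosed on time at Cycle 6 has been delayed by zero days. This stands. A reader might infer that every Cohort 3 subject reaching Cycle 6 must be stopped. The documents do not support that: it would require ignoring the word for delay in the criterion. The reply does not help the subject in step 3, who is in a genuine delay.

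A reader might also infer that Cohort 2's planned washout breaches the limit. It does not, because 6 weeks is not more than 6 weeks. A visit on day 43 or 44 for scheduling reasons could use the non-drug-related exception, with medical monitor approval.

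Nor is it right that there is no tolerance at Cycle 6, or that Section 5.5.1 makes stopping absolute. Section 5.5.1 defers to the stated exceptions, steroid tapers are covered, and Section 5.5.2 has its approval route. That route is most naturally read as a further exception for subjects who meet no other stopping criterion. What remains is that Section 5.5.4 omits it.

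Finally, one might conclude that Cohort 1 has two weeks of slack and the other cohorts none. That comparison is unsafe. With restart at the next routine visit, one skipped 4-weekly dose gives 28 + 28 = 56 days between doses in any cohort, and from Cycle 6 all three cohorts are on that interval.

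**Conclusion.** The point holds as an unresolved inconsistency. Section 5.5.4 read literally, with its clock starting at the last dose, puts a Cohort 3 subject held at Cycle 6 about 14 days (12 to 16) past the limit on the first day of the hold. In Cohort 2 the margin is zero (2 days inside to 2 days outside). The result assumes that the hold is for a drug-related event and involves no prolonged steroid taper. Otherwise an exception may apply.

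The number of subjects affected cannot be derived from the documents. It depends on how many of the up to approximately 30 per cohort reach Cycle 6 and how many then need a hold.

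The consequences are limited to discontinuation, exposure and deviation classification around Cycle 6, mainly in Cohort 3. A reader might infer that the adverse-event window differs by cohort, but its length is 100 days after discontinuation for everyone. DLT assessment, the expansion rule, alpha and power are unaffected.

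**What to change.** Reconcile Sections 5.5.1, 5.5.2 and 5.5.4 with Table 2 and Section 6.4.5 in an amendment:

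- State one start for the clock and use the same wording in all three sections.
- Say explicitly how the planned 6- and 8-week washouts count, both for a hold at Cycle 6 and for an adverse event that arises late in the washout.
- Give one common list of exceptions, so that the Section 5.5.2 approval route and the Section 5.5.4 list agree.

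The length of the limit and the conditions for resuming are clinical decisions for the sponsor. The cost is amendment wording. No extra data, visits or subjects are needed.
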